2 EXECUTIVE SUMMARY

Title	Characterizing HIV-related Diastolic Dysfunction
Indication	HIV+ patients
Location	Approximately 12 clinical centers in the United States
Brief Rationale	
With the advent of highly active antiretroviral therapy (HAART), human immunodeficiency virus (HIV) type 1 infection has become a chronic disease. The proportion of patients expected to survive 5, 10, and 15 years after conversion in the HAART era are 99%, 93% and 89% respectively. With increased life expectancy and decreased morbidity from opportunistic infections, the importance of chronic complications associated with HIV-1 infection, including HF is becoming more evident. The advent of HAART has altered the epidemiology of HIV associated cardiomyopathy evolving from a primarily left ventricular systolic dysfunction to the growing recognition of left ventricular DD. DD is associated with the development of atrial fibrillation and heart failure (HF), and portends higher risk for all-cause mortality. Thus there is a widespread prevalence of cardiac abnormalities in HIV infected individuals that are associated with HF development and may represent a sub-clinical abnormality that may be potentially intervened upon to reduce the risk of subsequent HF. There are little data to understand the natural history and pathogenesis of cardiac abnormalities, specifically DD in HIV+ individuals, which may adversely affect the longevity and quality of life of these individuals.

Objective	To characterize the determinants, mechanisms, and consequences of diastolic dysfunction in patients with HIV infection
Patient Population	Approximately 200 HAART-treated virally suppressed HIV+ subjects (100 HIV+/DD+ & 100 HIV+/DD-)
Study Design	Multi-center, cross-sectional study

3 INTRODUCTION

3.1 Background and Significance

Heart failure (HF) patients have $\approx 50\%$ mortality risk within 5 year of diagnosis, underscoring the need to better understand determinants of HF risk in order to develop effective screening and prevention interventions. An emerging risk factor for HF is human immunodeficiency virus (HIV) infection. HIV-related HF was identified as a major priority by the 2015 NHLBI AIDS Working Group. Since the early reports from the 1980s, the pattern of left ventricular (LV) dysfunction in HIV has evolved. Studies in the modern anti-retroviral therapy (ART) era have demonstrated lower rates of LV systolic dysfunction¹ but strikingly higher rates of diastolic dysfunction (DD), ranging from 26-50% as compared to 6-30% in the general population.² The mean age of HIV+ subjects with DD ranged from 38-49 years,¹ which is at least a decade younger than DD onset in the general population.³ DD is associated with atrial fibrillation, HF, and mortality.⁴⁻⁶ Thus there is a concern that the next epidemic in HIV+ patients will be HF with preserved ejection fraction (HFpEF). There is an unmet need to study DD in HIV+ patients to understand why they develop more prevalent and early onset DD.

Diastolic Dysfunction and Heart Failure

Left ventricular (LV) diastolic dysfunction (DD) is frequently present in older adults, with a prevalence ranging from 6-30% depending on the methodology, definition, and population studied. DD is associated with the development of atrial fibrillation and heart failure (HF), and portends higher risk for all-cause mortality. Previous studies have shown that DD is associated with obesity, hypertension, and metabolic syndrome, conditions that are associated with elevated inflammatory cytokines and endothelial dysfunction. It is important to note that DD is not the same as diastolic heart failure or HF with preserved ejection fraction (HFpEF). DD (also known as subclinical DD or preclinical DD) is an asymptomatic pathophysiological abnormality that precedes overt, symptomatic HF. As such, it is a clear representation of ACC/AHA Stage B HF (asymptomatic cardiac structural and functional abnormalities). It is critically important to understand DD prevalence, pathogenesis, and sequelae given its association with significant morbidity and mortality.

HIV-Related Diastolic Dysfunction and Heart Failure

With the advent of highly active antiretroviral therapy (HAART), human immunodeficiency virus (HIV) infection has become a chronic disease. The proportion of patients expected to survive 5, 10, and 15 years after seroconversion in the current era are 99%, 93% and 89%, respectively. With this increased life expectancy, chronic complications including HF with preserved ejection fraction (HFpEF) are emerging. Contemporary HAART has altered the epidemiology of HIV-related cardiomyopathy from primarily LV systolic dysfunction (LVSD), reported in 7-20% of patients in earlier studies, to predominantly DD, reported in up to 50% of HIV patients. There are few data to understand the natural history and pathogenesis of the growing prevalence of DD in HIV+ subjects who are virally suppressed on optimal HAART therapy. The growing DD prevalence in HIV, and the link of DD with HFpEF and mortality, raise significant health concerns for these patients.

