Hypothesis: The broad representation of biological pathways included on the proteomic and metabolomic panels will enable identification of novel mechanisms underlying DD in HIV+ subjects.

Objective 3: Understand the consequences of diastolic dysfunction.

Aim 3a: To study the effect of DD on mechanics of the left atrium in HIV.

Hypothesis: HIV+/DD+ subjects will have blunted augmentation of left atrial strain during passive leg raise compared to HIV+/DD- and HIV-/DD+ subjects.

Aim 3b: To study the sub-clinical necrosis and myocardial stress in HIV+/DD+ subjects.

Hypothesis: HIV+/DD+ subjects will have higher troponin and NTproBNP levels than HIV+/DD- and HIV-/DD+ subjects.

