5 BASIC STUDY DESIGN

This is a multicenter clinical trial of a cross section of HIV+ patients with and without diastolic dysfunction. Sites currently participating in the Heart Failure Clinical Research Network (HFN) will collaborate with their HIV clinics to identify eligible patients. Approximately 200 HAART-treated virally suppressed HIV+ subjects (100 HIV+/DD+ & 100 HIV+/DD-) will be enrolled. Data will be managed by the HFN Coordinating Center (CC) at Duke University. This study will evaluate biomarkers, phenomapping, metabolomics, cMRI, echocardiography to determine characteristics unique to this patient population. This patient population will then be compared to the MESA (Multi-Ethnic Study of Atherosclerosis) population providing subjects who are HIV-/DD+ (see section 7.0).

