5.1 Screening Phase

Subjects who are HIV positive, have been on HAART for ≥ 6 months and are virally suppressed will be screened for participation in the study using the inclusion and exclusion criteria listed below. Eligible patients will be approached to consent to the study. Those who agree to participate will be screened with an echo to determine if they are EF eligible and classified as DD+ or DD-. Diastolic dysfunction criteria are:

- (1) LVEF $> 50\%$
- (2) Evidence of impaired LV relaxation (septal $e' < 7\text{cm/s}$ or lateral $e' < 10\text{cm/s}$)
- (3) Evidence of chronically elevated LV filling pressure or LVH (or concentric remodeling)
 - (a) LA volume index $> 28\text{ml/m}^2$ or

- (b) LV hypertrophy (LV mass index $>95\text{g/m}^2$ in women, $>115\text{g/m}^2$ in men or
- (c) Concentric LV remodeling (relative to wall thickness >0.42)

[figure not shown]

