6. LVEF $> 50\%$

7.2 Exclusion Criteria

1. Past EF $< 50\%$
2. Moderate or severe valve stenosis or regurgitation, or past repair or replacement
3. Percutaneous or surgical revascularization or active angina
4. Persistent atrial fibrillation
5. BP > 160 mmHg SBP or > 100 mmHg DBP
6. Comorbid inflammatory disease (e.g. RA or SLE)
7. Active cancer or cancer chemotherapy treatment in the prior year (except skin cancer that did not require chemotherapy or radiation)
8. Chronic use of steroids or anti-inflammatory therapy
9. GFR < 30 mL/min
10. Active in a clinical trial with investigational product
11. Pregnant or lactating females
12. Contraindication to cMR or gadolinium injection (such as severe claustrophobia, metal implants, etc.)

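### The protocol defines diastolic dysfunction as asymptomatic, but its eligibility rules do not exclude clinical heart failure with preserved EF

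*Combined protocol and SAP*

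**What the plan says.** **The condition under study.** Section 3.1 distinguishes DD from heart failure with preserved EF (HFpEF). It says that DD "is an asymptomatic pathophysiological abnormality that precedes overt, symptomatic HF" and that "it is a clear representation of ACC/AHA Stage B HF". In section 4, Aim 3b is "To study the sub-clinical necrosis and myocardial stress in HIV+/DD+ subjects", measured by troponin and NT-proBNP.

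**Who may enter.** Section 7.1 has six inclusion criteria, of which the only cardiac one is LVEF above 50%. Section 7.2 has twelve exclusions. The cardiac ones are a past EF below 50%, significant valve disease or valve surgery, "Percutaneous or surgical revascularization or active angina", "Persistent atrial fibrillation" and high blood pressure. Section 7.2.1 adds atrial fibrillation at the time of MRI, for the T1 substudy only. Sections 8.1 and 8.2 add the screening echo and a pregnancy test. No item names heart failure, its symptoms, NYHA class, or a heart failure admission or treatment.

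**How the groups are formed.** Section 5.1 assigns DD+ or DD- from the screening echo alone. DD+ needs preserved EF, a low e', and one of left atrial enlargement, LV hypertrophy or concentric remodeling.

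**What is collected.** Section 9.1 lists a general medical history, named comorbidities (heart failure is not among them) and the KCCQ. No section uses these to exclude, classify or adjust.

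**The HIV-negative comparator.** According to section 7, MESA participants were free of cardiovascular disease at enrollment in 2000-2002 and have been under surveillance for events, including heart failure, since then. No heart failure exclusion is stated for the Exam 6 subjects who will serve as HIV-/DD+.

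**The concern.** The protocol's description of DD and its entry rules do not select the same people. A patient with clinical HFpEF has preserved EF by definition, so the two EF criteria do not remove that patient, and he or she can meet every DD+ criterion. The remaining cardiac exclusions make this less likely but do not prevent it.

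Heart failure patients on one side of the contrast would tend to raise NT-proBNP, troponin and fibrosis and to lower left atrial reserve, which is the direction of the study hypotheses. A positive finding could then not be credited wholly to a pre-clinical abnormality, and that is the reading on which Aim 3b and the prevention rationale depend. As written, the plan would neither limit nor report how many such subjects there are.

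**Working it through.** **1. Reproduce the plan's figures.** Section 13.2 assumes 100 per group, a two-sample t-test and two-sided alpha 0.05. By the normal approximation, the standard error of a difference in SD units is sqrt(2/100) = 0.1414.
- 0.40 SD: 0.40/0.1414 = 2.83, and Phi(2.83 - 1.96) = 80.7%.
- 0.46 SD: 0.46/0.1414 = 3.25, and Phi(3.25 - 1.96) = 90.2%.
- Log IL-6 (SD 0.75): 80.7% for 0.30 and 91.0% for 0.35.

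The exact t-test gives 80.4%, 89.9%, 80.4% and 90.7% in the same order. The stated power is right and is not in dispute.

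**2. Can a patient with clinical HFpEF be enrolled as DD+?** LVEF above 50%: met. Past EF below 50%: need not apply. Valve disease, revascularization or angina, persistent atrial fibrillation, blood pressure, GFR: each may be absent. Low e' with a structural sign: can be met. Symptoms or a heart failure diagnosis: not asked. So such a patient can enter.

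**3. What would that do to the comparison?** The documents give neither the share of such patients nor how far their markers differ. Both are assumptions here.

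Let f be the share of DD+ with clinical heart failure and h their marker excess in SD units. Suppose there are none in DD- and that asymptomatic DD+ truly equals DD-. Then:
- shift in the DD+ mean: b = f x h
- variance in DD+: v = 1 + f(1 - f)h²
- standard error: se = sqrt(1/100 + v/100)
- rejection rate: Phi(b/se - 1.96) + Phi(-b/se - 1.96)

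Worked case, f = 10% and h = 2: b = 0.20; v = 1 + 0.09 x 4 = 1.36; se = sqrt(0.0236) = 0.154; b/se = 1.30; rejection rate about 26%.

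| f | h | Shift (SD) | Share of 0.40 SD | Rejection rate |
|---|---|---|---|---|
| 2% | 1 | 0.02 | 5% | 5.2% |
| 5% | 1 | 0.05 | 12.5% | 6.4% |
| 5% | 1.5 | 0.075 | 19% | 8.1% |
| 10% | 1.5 | 0.15 | 37.5% | 17.3% |
| 10% | 2 | 0.20 | 50% | 26% |

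**4. If DD- also contains heart failure.** The shift becomes (share in DD+ minus share in DD-) x h. With 10% and 5% at h = 1.5 it is 0.05 x 1.5 = 0.075 SD, half the 0.15 SD in the table.

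**5. Which markers?** For log IL-6, an excess of 1.5 to 2 SD is 1.5 x 0.75 = 1.125 to 2 x 0.75 = 1.5 log units. If the log is natural (the base is not stated), that is about a 3- to 4.5-fold higher level. Nothing in the documents supports so large an excess for IL-6, so the lower rows are more relevant to NT-proBNP, troponin, left atrial strain and fibrosis.

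**The case against.** The strongest reply is that the effect may be very small. Every input is assumed, and at a 2% to 5% share with a 1 SD excess the rejection rate is 5% to 6%, close to nominal. The existing cardiac exclusions also make overt heart failure less common. This stands: the documents do not show that the bias is large.

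The scope can also be defended. The asymptomatic wording is in the background section, section 3.2 hopes to inform the progression of DD to HFpEF, and Objective 3 concerns consequences. A broad cohort defined by echo is a legitimate choice. But it does not fit the sub-clinical wording of Aim 3b, and the plan does not say that it chose this breadth.

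Five stronger readings are tempting, and the documents do not support them:
- *Recruitment from heart failure clinics makes such patients common.* The network sites are heart failure sites, but section 5 says "Sites currently participating in the Heart Failure Clinical Research Network (HFN) will collaborate with their HIV clinics to identify eligible patients". Subjects are sought for treated, suppressed HIV.
- *Nearly all such patients would be DD+.* DD+ needs both a low e' and a structural sign, so a heart failure patient lacking either is not DD+. More often in DD+ is plausible; almost only in DD+ is not shown.
- *A share of 20%, which would give a rejection rate of 50% or more.* No figure in the documents points to such a share.
- *The type I error is inflated.* For the contrast of echo-defined groups, a difference due to heart failure is real. What suffers is its attribution to pre-clinical disease. The calculation is also unadjusted, whereas the primary analysis uses inverse probability weighting with covariates not yet listed.
- *Heart failure history is already recorded.* Section 9.1 lists medical history in general terms only.

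**Conclusion.** The inconsistency is real. DD is described as asymptomatic Stage B disease, and one aim is framed as sub-clinical, yet clinical heart failure with preserved EF is nowhere excluded. Following the protocol exactly could therefore move the DD+ versus DD- contrast toward the hypotheses, mainly for NT-proBNP, troponin, left atrial strain and fibrosis.

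The size cannot be determined from the documents. Under the assumptions above it runs from negligible (about 5% rejection) to material (17% to 26%, with a shift of 0.15 to 0.20 SD). Heart failure in DD- would reduce it. In comparisons with HIV-/DD+ the direction is open, because MESA subjects may have developed heart failure since enrollment.

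This does not make the planned tests invalid or show that the results will be misleading. It is a gap worth closing because closing it costs little.

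**What to change.** 1. Add a clinical diagnosis of heart failure, at any EF, to the exclusions in section 7.2.
2. For subjects already enrolled, state in the SAP, which section 13.1 says will be completed before analysis, that those with a clinical heart failure diagnosis in the baseline medical history are left out of the primary DD+ versus DD- comparisons, in both groups. Report a sensitivity analysis that includes them, and give their number by group.
3. Confirm that the medical history form records heart failure. If it does not, add the item.
4. Apply the same rule to the MESA HIV-/DD+ group, using its heart failure surveillance.

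**Cost.** One eligibility line or one analysis-population rule, and possibly a few fewer DD+ subjects. If 5 of 100 left DD+ and none left DD-, the difference detectable with 80% power would grow by sqrt((1/95 + 1/100)/(2/100)) = 1.013, from 0.40 to about 0.405 SD. If 10 left, the factor is sqrt((1/90 + 1/100)/(2/100)) = 1.027, giving about 0.41 SD.

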3.2 Preliminary Studies

Earlier studies reported a prevalence of left ventricular systolic dysfunction between 7.5% and 20%.¹ A recent study showed that 32% of well controlled HIV infected patients had a left ventricular ejection fraction of 45-55% and only 2.3% had an EF<45%, but DD was present in

48%.¹ Hsue⁹ et al found only 4% of patients had ejection fraction <50%, whereas 49% had DD, and Schuster⁷² et al found that 13% of patients had an ejection fraction <50% but 64% had DD. A meta-analysis of 11 studies in the HAART era assessed 2242 well-controlled, asymptomatic HIV-1 infected patients, and reported a prevalence of left ventricular systolic dysfunction of 8.3% and left ventricular DD of 43.4%.² Recent studies using MRI in small cohorts of HIV+ patients suggest that treated and suppressed HIV infection is associated with myocardial inflammation, fibrosis and LV dysfunction.^{7,8} Furthermore, the editorial accompanying these studies called for studies that correlate biomarkers, imaging and tissue samples to understand the underlying mechanism of the findings.⁹

[figure not shown]
Thus there is a widespread prevalence of cardiac abnormalities in HIV infected individuals that are associated with HF development and may represent a sub-clinical abnormality that may be potentially intervened upon to reduce the risk of subsequent HF. There are little data to understand the natural history and pathogenesis of cardiac abnormalities, specifically DD in HIV+ individuals that may adversely affect their longevity.

A new theoretical framework for understanding diastolic dysfunction and HFpEF postulates a central role for inflammation in the progression of disease.¹⁰ It has been hypothesized that many of the cardiovascular abnormalities in HFpEF can be understood as the downstream consequence of the pro-inflammatory state associated with diseases such as obesity, hypertension, diabetes, chronic obstructive pulmonary disease, anemia, and chronic kidney disease.¹⁰ Because of their heightened state of inflammation that begins at the time of infection¹¹, HIV-infected people may present a unique model to better understand the inflammation hypothesis in HFpEF, and provide insight on the pathogenesis and progression of diastolic dysfunction and HFpEF in all populations. Because there are no evidence-based therapies for HFpEF, novel studies examining HFpEF in the HIV population may provide critical knowledge that helps solve the puzzle of how to treat this perplexing disease.

4 OBJECTIVES AND HYPOTHESIS

Multiple domains of biomarkers (fibrosis and remodeling, arterial inflammation, hypercoagulability and oxidative stress), proteomic and metabolomics analyses, and other cardiac structural and functional changes will be harnessed to elucidate the mechanistic pathways leading to DD in HIV. Exploratory analyses will assess if DD in HIV is associated with higher wall stress and the potential microvascular dysfunction in these patients leads to subclinical myocardial necrosis.

FIGURE 1

The overarching objective of this protocol is to study the determinants, mechanisms, and consequences of DD in HIV infected individuals.

Objective 1: Understand the determinants of diastolic dysfunction

Aim 1a: To compare persistent inflammation between HIV+/DD- and HIV+/DD+ subjects.

Hypothesis: HIV+/DD+ subjects will have greater levels of pro-inflammatory cytokines (IL-6, hsCRP) than HIV+/DD- subjects despite ART and viral suppression

Aim 1b: To compare immune activation between HIV+/DD- and HIV+/DD+ subjects.

Hypothesis: HIV+/DD+ persons will have greater immune activation (sCD163; sCD14; CD14 and CD16 expression; and T cell activation and subsets: Th1, Threg, CD4+, CD8+ T cell activation) than HIV+/DD- subjects.

Aim 1c: To compare inflammation between HIV+/DD+ and HIV-/DD+ subjects.

Hypothesis: HIV+/DD+ persons will have greater inflammation (IL-6, hsCRP) than HIV-/DD+ subjects.

Aim 1d: Perform phenomics of aggregate demographic, clinical, biomarker, electrocardiogram, and imaging data to define risk factor phenotype signatures, and relate these to HIV+/DD+ vs. HIV-/DD+.

Hypothesis: Specific pheno-groups will be associated with HIV+/DD+ and will differ from HIV-/DD+.

Objective 2: Understand the mechanisms of diastolic dysfunction

Aim 2a: To compare myocardial fibrosis by magnetic resonance imaging between HIV+/DD+ and HIV+/DD- subjects.

Hypothesis: HIV+/DD+ persons will have greater fibrosis burden than HIV+/DD- persons.

Aim 2b: To identify systemic determinants of DD in HIV+ persons.

Hypothesis: HIV+/DD+ persons will have higher serum levels of biomarkers of fibrosis and remodeling, arterial inflammation, oxidative stress, and hypercoagulability than HIV+/DD- or HIV-/DD+ subjects.

Aim 2c: To study the proteomic and metabolomic profile of HIV+/DD+ subjects.

Hypothesis: The broad representation of biological pathways included on the proteomic and metabolomic panels will enable identification of novel mechanisms underlying DD in HIV+ subjects.

Objective 3: Understand the consequences of diastolic dysfunction.

Aim 3a: To study the effect of DD on mechanics of the left atrium in HIV.

Hypothesis: HIV+/DD+ subjects will have blunted augmentation of left atrial strain during passive leg raise compared to HIV+/DD- and HIV-/DD+ subjects.

Aim 3b: To study the sub-clinical necrosis and myocardial stress in HIV+/DD+ subjects.

Hypothesis: HIV+/DD+ subjects will have higher troponin and NTproBNP levels than HIV+/DD- and HIV-/DD+ subjects.

4.1 Exploratory Objectives

Exploratory analyses will assess if DD in HIV is associated with higher wall stress and the potential microvascular dysfunction in these patients leads to subclinical myocardial necrosis.

A common pool of uncommitted resources will be used to solicit further ancillary sub-studies. These studies may be related to focus on other populations (e.g. HIV+ subjects without viral suppression), assessment of other novel immune activation markers or viral DNA or residual replication, gut microbiome and its association with DD, arterial stiffness and endothelial function, and epicardial, myocardial, and visceral fat distribution, and skeletal muscle function in HIV patients with and without DD.

5 BASIC STUDY DESIGN

This is a multicenter clinical trial of a cross section of HIV+ patients with and without diastolic dysfunction. Sites currently participating in the Heart Failure Clinical Research Network (HFN) will collaborate with their HIV clinics to identify eligible patients. Approximately 200 HAART-treated virally suppressed HIV+ subjects (100 HIV+/DD+ & 100 HIV+/DD-) will be enrolled. Data will be managed by the HFN Coordinating Center (CC) at Duke University. This study will evaluate biomarkers, phenomapping, metabolomics, cMRI, echocardiography to determine characteristics unique to this patient population. This patient population will then be compared to the MESA (Multi-Ethnic Study of Atherosclerosis) population providing subjects who are HIV-/DD+ (see section 7.0).

